## 4 Statistical analyses and presentation of data

### 4.1 General considerations

The data from the clinical assessments will be summarised by feeder study, grand total and time point using descriptive techniques. Summary statistics (n, arithmetic mean, standard deviation, median, minimum and maximum values) will be presented for continuous variables (absolute values at each time point and, if relevant, changes from baseline) and counts and, if relevant, percentages will be presented for categorical variables. Where appropriate, the presentation of results will include confidence intervals of estimated effects and plots.

The following rules for displayed number of decimal places are considered for listings and tables:

- Actual values and change from baseline: Same number of decimal places as in data.
- Percentage change from baseline: One decimal place.
- Mean, median, SD, minimum and maximum: Same number of decimal places as in data.

Values below LLOQ are displayed in tables and listings and used in calculations as the LLOQ value.

All data will be listed. Patients will be identified by a two-level number: xx-yyy where xx = number of the feeder study and yyy = patient ID in the feeder study.

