6.2.8 Immunogenicity by Anti-Drug Antibodies (ADA)

Samples for the determination of anti-drug antibody (ADA) levels in serum will be analysed for anti-imlifidase IgG using a customized imlifidase ImmunoCAP test. The analysis will be performed at the central laboratory, ThermoFisher Scientific, Immuno Diagnostics, Service Laboratory, Allerød, Denmark. Full details of the analytical method used, and the analysis results will be detailed in a separate bioanalytical report. The ADA samples will be taken at the times presented in the study flow chart. The date and time of collection of each sample will be recorded on the laboratory requisition form and in the CRF.

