## **ADA**

The anti-imlifidase IgG will be tabulated by 1, 2, 3 and 5 years.

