### 9.1 Tables.

Table 14.1.1. Patient disposition, including reason for discontinuation.

Table 14.1.2. Demography and body measurements.

Table 14.1.3. Transplant characteristics.

Table 14.1.4. Immunosuppressive medication.

Table 14.1.5. Protocol deviations.

Table 14.1.6. Comorbidity.

Table 14.2.1. Summary of overall graft survival.

Table 14.2.2. Summary of overall graft survival not censored for death.

Table 14.2.3. Overall patient survival.

Table 14.2.4. Kidney function parameters.

Table 14.2.5. Biopsy proven acute rejection episodes.

Table 14.2.6. Antibody mediated rejections.

Table 14.2.7. Graft rejection episodes (treatment).

Table 14.2.8. Graft rejection episodes (number).

Table 14.2.9. Graft rejection episodes (procedure).

Table 14.2.10. EQ-5D-5L.

Table 14.2.11. EQ-5D-5L (Detailed).

Table 14.2.12. KDQOL-SF 1.3.

Table 14.2.13. DSA level assessment (evaluated locally)

Table 14.2.14. DSA level assessment (evaluated by Hansa Biopharma)

Table 14.2.15. BK-Virus.

Table 14.3.16. AE overview.

Table 14.3.17. AE by SOC and Pt.

Table 14.4.1. ADA (IgG).

Table 14.4.2. Clinical chemistry (only IgG).

Table 14.4.3. Haematology.

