## 9.2 Listings

Listing 16.2.1.1. Patient disposition - All transplanted patients.

Listing 16.2.2.1. Protocol deviations.

Listing 16.2.3.1. Patients excluded from the efficacy analysis.

Listing 16.2.4.1. Demography and body measurements.

Listing 16.2.4.2. Immunosuppressive medication .

Listing 16.2.4.3. Study Dates.

Listing 16.2.4.3. Comorbidity.

Listing 16.2.6.1. Graft status.

Listing 16.2.6.2. Dialysis.

Listing 16.2.6.3. Overall graft survival.

Listing 16.2.6.4. Reason for graft loss.

Listing 16.2.6.5. Graft loss not censored for death.

Listing 16.2.6.6. Patient Survival.

Listing 16.2.6.7. Kidney function.

Listing 16.2.6.8. Kidney biopsy findings.

Listing 16.2.6.9. Graft rejection episodes (treatment).

Listing 16.2.6.10. Graft rejection episodes (number).

Listing 16.2.6.11. Graft rejection episodes (procedure).

Listing 16.2.6.12. Comorbidity.

Listing 16.2.6.13. DSA level assessment (evaluated locally)

Listing 16.2.6.14. DSA level assessment (evaluated by Hansa Biopharma)

Listing 16.2.6.15. HLA antibodies (MFI) including HLA mismatches-potential DSA (central evaluation).

Listing 16.2.6.16. HLA antibodies (MFI) mismatches-potential DSA (central evaluation).

Listing 16.2.6.17. EQ-5D-5L.

Listing 16.2.6.18. KDQOL-SF 1.3.

Listing 16.2.6.19. BK virus.

Listing 16.3.1. Adverse event overview.

Listing 16.3.2. Adverse event by SOC and PT

Listing 16.3.3. Serious AEs.

Listing 16.3.4. AEs leading to death.

Listing 16.3.5. AEs leading to withdrawal.

Listing 16.4.1. Clinical Chemistry (only IgG).

Listing 16.4.2. Haematology (haemoglobin).

Listing 16.4.3. Haematology (difference of leukocytes).

Listing 16.4.4. Haematology (thrombocytes).

Listing 16.4.5. ADA (IgG).

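### SAP 4.1 prints and analyses every result below the LLOQ as the LLOQ itself, so unquantifiable anti-imlifidase IgG results look measured and their mean can only be biased upward

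*SAP*

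**What the plan says.** SAP 4.1 (General considerations) states: "Values below LLOQ are displayed in tables and listings and used in calculations as the LLOQ value". The rule is general, so it covers ADA and any other assay with an LLOQ.

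The same section fixes what the rule feeds: "Summary statistics (n, arithmetic mean, standard deviation, median, minimum and maximum values) will be presented for continuous variables", given as "absolute values at each time point and, if relevant, changes from baseline". A count or percentage below LLOQ is not among the statistics, and neither is a geometric mean.

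For ADA, SAP 4.4.2 says only this: "The anti-imlifidase IgG will be tabulated by 1, 2, 3 and 5 years". It makes no exception to the general rule and gives no positivity cut-point and no sensitivity summary. SAP section 9 names a table (14.4.1), a listing (16.4.5) and a box plot (Figure 14.3.1) for ADA, and none of the titles mentions results below quantification.

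Protocol 6.2.8 says that samples "will be analysed for anti-imlifidase IgG using a customized imlifidase ImmunoCAP test". It gives no LLOQ and adds: "Full details of the analytical method used, and the analysis results will be detailed in a separate bioanalytical report". The protocol has no rule for values below the LLOQ.

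**The concern.** The sentence in SAP 4.1 does two things.

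- **Display.** A result known only to lie somewhere under the limit is printed as the limit. A reader of Listing 16.4.5 cannot tell which subjects were unquantifiable, so the listing no longer shows the result the laboratory reported. This needs no assumption about distributions and applies from the first such sample.
- **Calculation.** Each below-limit result enters the summaries at its largest possible value. The mean moves in one direction only, the spread is compressed, and the minimum becomes the LLOQ. The median and the lower edge of the box plot become the LLOQ once enough values are below it.

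Immunogenicity is a secondary objective of its own (SAP 1.1.1), and ADA is a listed secondary endpoint (SAP 1.1.2). The study is descriptive throughout, so the tables, listings and plots are the result, and no later model would correct them. At stake is whether a reader can see how many subjects have quantifiable antibody at each visit.

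**Working it through.** **No figure to reproduce.** The documents state no LLOQ, no expected share below it and no ADA mean. The direction of the effect can be derived. Its size can only be illustrated.

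**Inputs from the documents.** Substitution at the LLOQ for both display and calculation (SAP 4.1); arithmetic mean, SD, median, minimum and maximum (SAP 4.1); at most 46 subjects (SAP 2.2); no testing (Protocol 11.5).

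**Step 1: direction and bound, with no distribution assumed.** Let L be the LLOQ and p the share of values below it.

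- Bias of the mean = p × (L − mean true value of those below L).
- This is above zero whenever any value lies below L. Because concentrations cannot be negative, it is at most p × L.
- The bound is therefore 0.05L, 0.10L, 0.25L and 0.50L for p = 5%, 10%, 25% and 50%. Out of 46 subjects those shares are 2.3, 4.6, 11.5 and 23.
- Raising the lowest values to a common floor moves no two values further apart, so the SD can only stay the same or fall.

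**Step 2: order statistics.** The minimum prints as L as soon as one value is below it. The median is unaffected while fewer than half are below, and prints as L when more than half are. If the box edges are quartiles (the usual convention, which the SAP does not state), the lower edge prints as L once more than a quarter are below.

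**Step 3: size under an assumed log-normal distribution.** Set L = 1 and let s be the log-SD. With Φ the normal distribution function and z_p its p-quantile:

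- log-mean μ = −s·z_p, and true mean m = exp(μ + s²/2)
- contribution of values below L to the mean: B = m·Φ(z_p − s)
- relative bias = (p − B)/m

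Worked case, s = 1.0 and p = 50%: μ = 0; m = exp(0.5) = 1.649; B = 1.649 × Φ(−1) = 1.649 × 0.1587 = 0.262; bias = 0.500 − 0.262 = 0.238; 0.238/1.649 = 14.5%.

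Inflation of the arithmetic mean with the SAP rule:

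| Share below LLOQ | log-SD 0.5 | log-SD 1.0 | log-SD 1.5 |
|---|---|---|---|
| 5% | +0.3% | +0.2% | +0.1% |
| 10% | +0.9% | +0.6% | +0.2% |
| 25% | +3.7% | +3.0% | +1.5% |
| 50% | +13.3% | +14.5% | +9.6% |

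The SD at 50% below is understated by 18.9%, 5.6% and 0.9% for log-SD 0.5, 1.0 and 1.5.

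**Step 4: would half the LLOQ be better?** Not reliably. At log-SD 0.5 and 30% below, m = 1.473 and B = 0.225.

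- Substituting L: (0.300 − 0.225)/1.473 = +5.1%.
- Substituting L/2: (0.150 − 0.225)/1.473 = −5.1%.

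The errors are equal in size and opposite in sign. At 50% below, L/2 gives −8.8%, −0.7% and +1.4% for the three log-SDs. It often does better, but the sign of its error depends on an unknown distribution, whereas L always gives an upper bound.

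**The case against.** The strongest reply is that the effect may be nil. If no ADA result, or very few, falls below the LLOQ, nothing in the summaries moves noticeably, and the documents do not say that many will. ADA is one descriptive secondary endpoint, with no test in the study and no formal decision tied to the yearly reports (SAP section 5). The bias also overstates residual antibody, so it does not make immunogenicity look smaller. All of this stands and keeps the point minor. It does not answer the display fault, which does not depend on how many results are affected.

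Three stronger readings are tempting, and the documents do not support them.

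- **That the share below quantification will never be reported.** The output shells are held in a separate document (SAP section 8), and Protocol 6.2.8 sends assay results to a separate bioanalytical report. Neither was available, and either might show the share. What can be said is that the SAP does not require it. SAP section 9 treats templates as working documents that may change after signature, so they do not replace a rule in the SAP.
- **That the rule hides a fall in ADA, and that such a fall is the study's question.** The objective is an assessment of immunogenicity, and SAP 4.4.2 plans tabulation by year. Change from baseline appears in SAP 4.1 only where relevant. SAP 2.4 lists ADA among the feeder-study data without time points, although it gives them for SAB-HLA and kidney function. If a change were tabulated, a floor at the LLOQ would understate any movement across it, but that analysis is an inference.
- **That the distortion is far larger on a geometric scale.** The SAP plans no geometric mean, so such figures would describe a summary that will not be produced.

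**Conclusion.** The rule in SAP 4.1 is wrong as written, and the consequence is minor. Two conclusions need no assumption beyond the plain reading of the sentence: a below-limit result cannot be told apart from one measured at the limit in the SAP's own outputs, and the arithmetic mean can be biased only upward, by at most p × L.

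The actual size is unknown. The percentages rest on an assumed log-normal distribution with log-SD 0.5 to 1.5 and on assumed shares below the LLOQ: under 1% at 10% or less, about 1.5 to 4% at 25%, and about 10 to 15% at 50%. The display problem matters more than the mean in most of that range. The scope is descriptive secondary and safety summaries for any assay with an LLOQ.

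**What to change.** Amend the sentence in SAP 4.1 and the affected shells as follows:

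1. Show results below quantification as '<LLOQ' in listings, with the numerical limit stated.
2. Add a row with n (%) below LLOQ at each visit to Table 14.4.1 and to any other table affected.
3. Print the median and minimum as '<LLOQ' where they fall below the limit, and mark the LLOQ on the box plot.
4. Keep the stated substitution for means, and footnote the mean as an upper bound.

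With p and L both visible, a reader can bound the sample mean without a model: it lies between the printed mean minus p × L and the printed mean. Changing the substitute to half the LLOQ is not recommended. It exchanges one convention for another, and a median printed as half the LLOQ would be just as unmeasured.

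The cost is a revised sentence, a table row, a footnote and a reference line on the plot. No new data are needed.

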### 4.2 Subject disposition

The number of subjects in FAS will be summarized by feeder study. All 46 subjects from feeder studies that are eligible for the extension study will be accounted for. Furthermore, the number of subjects who withdraw from this study will be summarised overall, by withdrawal time, by reason for withdrawal and by feeder study.

### 4.3 Demographics and other baseline characteristics

The age, sex, race, country, site, height, weight and BMI will be summarised by feeder study.

Transplant characteristics will be tabulated.

Current immunosuppressive medication will be summarised by WHO drug version 153E, level 4 (chemical/therapeutic/pharmacological subgroup) called “medication class” in output, and by level 5 (chemical substance) called “medication name” in output.

Since this is a non-interventional follow-up study exposure and compliance are not applicable.

A summary of the protocol deviations will be presented.

### 4.4 Endpoints

#### 4.4.1 Primary endpoint

The primary endpoint, overall graft survival, is defined as time from transplantation to graft loss evaluated at 1, 2, 3 and 5 years after first dose of imlifidase. Graft loss is defined as: Permanent return to dialysis for at least 6 weeks, re-transplantation or nephrectomy. If dialysis is used to

define graft loss, the date of graft loss will be the first day of the last ongoing dialysis period reported. The graft loss is evaluated at 1, 2, 3, and 5 years after dosing, but the time will be recorded as duration in days.

The primary endpoint will be analysed by the Kaplan-Meier survival method for the combined group with all feeder studies. The overall graft survival will be tabulated and presented graphically as a KM plot with 95% confidence limits, indicating the risk set per year and marking the censored observations. The following events will be censored at the time of occurrence: withdrawal from the study without graft loss, death not caused by graft loss, evaluation time point (the yearly evaluations - only for the annual reports not in the final reporting of the study) and end of study without graft loss. The survival percentage with 95% CI will be estimated at 1, 2, 3 and 5 years, or, for the yearly summary analyses as far as data allows.

The reason for graft loss will be displayed in a listing.

The protocol stipulates that explorative modelling of the influence of covariates on the graft loss may be defined in the SAP. With a maximum sample size of 46 patients and an expected small proportion of patients with graft loss, estimation of covariate parameters may be highly variable in which case the explorative modelling will not be performed.

#### **4.4.2 Secondary endpoints**

##### **Graft loss not censored for death**

This endpoint is defined as the primary endpoint except that death for any cause also counts as a graft loss and therefore this event will not be censored in this case. The endpoint will be analysed and presented as the primary endpoint.

##### **Overall patient survival**

The overall patient survival is defined as time from transplantation to death for any cause. This endpoint will be analysed and presented as for the primary endpoint. The following events will be censored at the time of occurrence: withdrawal from the study while alive, evaluation time point (the yearly evaluations) and end of study while alive.

##### **Kidney function**

The kidney function is evaluated by the three parameters eGFR, P-creatinine and proteinuria. The parameters are all presented together with the safety laboratory tests. Each variable will be tabulated by feeder study and total and by visit.

The eGFR will be calculated as described in the MDRD equation (1):

$$\text{eGFR (mL/min/1.73 m}^2\text{)} = 175 \times (\text{Cr})^{-1.154} \times (\text{Age})^{-0.203} \times (0.742 \text{ if female}) \times (1.212 \text{ if African American}),$$

where Cr stands for creatinine value. This formula assumes that Cr is given in the mg/dL unit.

##### **Number of graft rejection episodes**

The number of graft rejection episodes following the Banff classification will be tabulated by 1, 2, 3 and 5 years, feeder study and grand total.

The Banff score from biopsies will be listed.

## **Treatment of graft rejection episodes**

The treatment of graft rejection episodes will be summary tabulated by 1, 2, 3 and 5 years and by treatment type. Examples of treatment types are dialysis episodes, plasmapheresis and medication.

## **Comorbidity**

Medically relevant comorbidities are e.g. infections, malignancy, diabetes mellitus, and cardiovascular events. These events will be tabulated at 1, 2, 3 and 5 years by comorbidity type.

## **DSA levels**

DSA levels will be evaluated by SAB-HLA at 1, 2, 3 and 5 years. The DSA levels will be, listed, summarized in a table and presented graphically.

## **BK virus**

The presence of BK virus along with clinically significance (yes/no) will be tabulated at 1, 2, 3 and 5 years.

## **ADA**

The anti-imlifidase IgG will be tabulated by 1, 2, 3 and 5 years.

## **4.5 Safety**

### **4.5.1 Adverse events**

Adverse events (AEs) will be classified according to the Medical Dictionary for Regulatory Activities (MedDRA) version 20.0.

As there is no treatment in this study and as all patients have previously been treated with imlifidase, there will be made no distinction between treatment emergent and non-treatment emergent adverse events. All recorded AEs will be included in the presentation.

An AE overview summary table will be prepared including the number of subjects reporting an AE, the percentage of subjects (%) with an AE, and the number of events (E) reported for the following categories:

- All AEs
- Deaths
- Serious adverse events (SAEs)
- AEs leading to withdrawal
- Severe and life-threatening AEs

AEs will be summarised in a table by MedDRA system organ class (SOC) and preferred term (PT). The table will display the total number of subjects reporting an AE, the percentage of subjects (%) with an AE and the number of events (E) reported. AEs will be presented by SOC sorted alphabetically and PT sorted in decreasing frequency of occurrence.

Additional tables may be prepared if more than 20 events are recorded.

**Data listings will be provided for:**

- All AEs sorted by subject number
- All AEs sorted by MedDRA Preferred Term
- SAEs
- AEs leading to death
- AEs leading to withdrawal

#### **4.5.2 Other safety endpoints**

The safety laboratory parameters will be presented in summary tables by feeder study and visits. In addition, the parameters will be listed and presented by box plots.

### **4.6 Other endpoints**

Two quality of life questionnaires will be used. The EQ-5D-5L is a general health questionnaire. The KDQOL-SF version 1.3 is a kidney specific questionnaire including a general health part as well.

The EQ-5D-5L will be presented by summarising the 5 individual items (mobility, self-care, usual activities, pain/discomfort, anxiety/depression), the VAS score and the overall derived index value by feeder study and visit.

The KDQOL-SF 1.3 will be presented by summarising the scales in the kidney disease (burden of kidney disease, quality of social interaction, cognitive function, symptoms/problems, effects of kidney disease, sexual function, sleep, social support, work status, dialysis staff encouragement) and SF-36 (Physical functioning, Role limitations—physical, Pain, Emotional well-being, Role limitations—emotional, Social function, Energy/fatigue, General health) parts of the questionnaire including the composite scores. Tabulation will be by feeder study and visit.

## 5 Interim analyses

This is a prospective long-term follow-up study. The accumulating data collected is planned to be presented yearly. As there is no formal decision associated with these reports, there are no multiplicity issues and the yearly reports will be presented as is. Interim analyses will focus on the primary endpoint and selected secondary endpoints evaluating efficacy parameters.

## 6 Deviations from protocol analysis

The secondary endpoint graft loss not censored for death meaning ‘survival free of graft loss as well as death’ is not listed as an endpoint in the protocol (version 4.0 incl. Amend 03), but is only mentioned in section 11.6.1 Graft loss not censored for death.

## 7 Quality control

The quality control of the data will be performed as follows:

- By [REDACTED] Data Management for all CRF data following the data validation plan
- By [REDACTED] Statistics and Programming for all data received as either Trial Master export or as import from central lab data

The QC depends on the process below, but it will follow [REDACTED] Single Use Programs:

SDTM data sets will be generated by programs in the Statistical analysis system (SAS) by reading in lab data and export data from Trial Master and converting to SDTM formats following the SDTM specifications. The QC will include:

- Independent Code review
- CRF annotation review vs SDTM content
- Run of Pinnacle verification
- QC of CRF input vs output in SDTM on a sample of data
- Format and fonts in annotated CRF

ADaM data sets will be based on the SDTM data sets. The programming of the ADaM datasets will be performed in SAS and QC of the programs will include

- Independent code review
- Run of Pinnacle verification
- QC of SDTM input data vs output in ADaM or listings

Tables, listings and figures (TLF) will be created by SAS programs and based on the ADaM data sets. The programming of TLFs will be reviewed by an independent person.

Since there are no formal statistical analyses double programming will not be applied in this study.

The programming and execution of programs for producing data sets and tables, figures and listings follow the [REDACTED] on standard programs, programming environment and single use programs respectively.

SAS version 9.4 or later and SAS Viya version 3.5 will be used for data handling and presentation.

## 8 Layout of output

TLF shells are presented in a separate document. The planned table of content will also be presented separately. The final output may deviate slightly as decisions on numbering and layout of TLF and similar may be updated after signature of this SAP.

The output will follow █ standard output templates. Tables and listings will first be prepared as individual RTF (Rich text format, which is a standard text format) files. This file type may be opened and saved in the currently available Microsoft Word versions. Graphical output will be prepared in PNG (Portable network graphics) format, which is the standard graphical format in current Microsoft software packages and therefore easily importable into Microsoft Word documents.

Tables and figures will per default be created in portrait format while listings will be in landscape format. Margins and font will be chosen to respect the requirements for filing with EMA (European medicines agency) and FDA (the US Food and drug administration).

The output items (tables, listings, figures) will be collected in Word documents as described in the TOC below. Separate Word documents will be created for tables (called 14.1), figures (called 14.2), and listings (called 16) respectively.

